9.1.1.2. Analysis of Subjects with a ≥ 4 -Fold Increase

The proportion of subjects with a ≥ 4 -fold increase in serum anti-RSV/A-, RSV/B-, hMPV/A-, hMPV/B-specific NAb (live-virus assays), RSV and hMPV IgG prefusion F protein-specific antibody titers will be calculated at Day 28 and summarized by vaccine group for each of the following: RSV-A, RSV-B, both RSV strains, either RSV strains, hMPV-A, hMPV-B, both hMPV strains, either hMPV strains, RSV and hMPV IgG prefusion F protein-specific antibody titers. The 95% CI of the difference in proportion of subjects with a ≥ 4 -fold increase in serum anti-RSV/A-, RSV/B-, hMPV/A-, hMPV/B-specific NAb (live-virus assays), RSV and hMPV IgG prefusion F protein-specific antibody titers between vaccine groups with and without adjuvant and IVX-A12a versus Placebo and IVX-A12d versus Placebo will be computed using Wilson's score method. Logistic regression models will be used to further describe the IVX-A12d response to vaccination when compared to IVX-A12a. Also, logistic regression models will be used to describe the response of IVX-A12a versus Placebo and the response of IVX-A12d versus Placebo. The outcome variable is binary (≥ 4 -fold increase or no ≥ 4 -fold increase). Vaccine group, log2 transformed baseline NAb titer, age stratification category, and gender are included as explanatory variables.

The ≥ 4 -fold increase analyses will be repeated for the following:

- By vaccine group and age subgroup analyses category. For the logistic regression models, vaccine group, log2 transformed baseline titer, age stratification category and gender are included as the explanatory variables;
- By vaccine group and baseline tertile; For the logistic regression models, vaccine group, age stratification category and gender are included as the explanatory variables;
- By vaccine group and age subgroup analyses and baseline tertile. For the logistic regression models, vaccine group, age stratification category and gender are included as the explanatory variables.

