Approximately 250 adult subjects (60 to 85 years of age) were enrolled. A subject was considered enrolled upon having signed the informed consent form (ICF). Subjects were randomly allocated to receive either IVX-A12 or placebo at a ratio 2:2:1, resulting in approximately 100 subjects in each IVX-A12 group and 50 in the placebo group. In addition, subjects were stratified by age groups (60 to 69 years of age versus 70 to 85 years of age).

Randomization occurred simultaneously into all three trial groups (IVX-A12a, IVX-A12d, and placebo). Initial vaccinations were performed in sentinel subjects and then expanded to the remaining subjects in each of the three trial groups. In total, there were 40 sentinel subjects. In each IVX-A12 group, 16 sentinel subjects received IVX-A12a (8 subjects from age stratum 60 to 69 years of age and 8 subjects from age stratum 70 to 85 years of age); 16 sentinel subjects received IVX-A12d (8 subjects from age stratum 60 to 69 years of age and 8 subjects from age stratum 70 to 85 years of age). In the placebo group, 8 sentinel subjects received placebo (4 subjects from age stratum 60 to 69 years of age and 4 subjects from age stratum 70 to 85 years of age). Sentinels were closely monitored for a minimum of 48 hours. If no stopping rules were triggered, the remaining subjects in the IVX-A12 and placebo groups were enrolled.

There are a total of seven scheduled clinic visits required for each subject (at screening, then Days 0, 7, 28, 90, 180, and 365), and five phone contacts (on Days 3, 14, 56, 135, and 270) for all subjects in the main part of the trial. IVX-A12a and placebo subjects consenting to the extension portion of the trial will have a phone contact at Day 545 for safety assessments and a clinic visit at Day 730 for safety assessments and blood sampling for immunogenicity.

The time and events schedules for the main study and for the extension are presented in [Section 2.1](#) and [Section 2.2](#), respectively.

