4.1. Brief Description

4.1.1. Main Trial Brief Description

The Phase 2a clinical trial of IVX-A12 is a randomized, observer-blind, placebo-controlled, dosage optimization, multi-center trial to evaluate the safety and immunogenicity of a single IM dose of two different formulations of IVX-A12 (IVX-A12a with diluent alone and IVX-A12d with MF59[®]) compared to placebo (diluent) in adults 60 to 85 years of age. The dosage level and formulation were selected based on the totality of the IVX-A12 nonclinical data and the interim safety and immunogenicity clinical data from the ongoing IVX-A12 Phase 1 clinical trial.

The main portion of this Phase 2a clinical trial will have three vaccine groups: Two IVX-A12 groups and one placebo group. The total amount of VLP in the two IVX-A12 groups will not exceed 300 µg of VLPs. IVX-A12a, IVX-A12d, or placebo will be administered as a single IM dose to older adult subjects enrolled into two age strata (adults 60 to 69 years of age and elderly adults 70 to 85 years of age). Eligible older adults will be randomized simultaneously to the different trial groups to ensure balance among the groups. This Phase 2a clinical trial includes a sentinel group of 40 subjects (16 subjects per active treatment group [n=32]; 8 subjects in the placebo group) to conservatively assess the 150 µg RSV/150 µg hMPV dosage level in combination with MF59[®]. Sentinel subjects were closely monitored for a minimum of 48 hours and, if no stopping rules were triggered, the remaining subjects were enrolled.

Approximately 250 subjects will be randomly allocated at a ratio of 2:2:1 to receive one of the two IVX-A12 formulations (IVX-A12a [N=100] or IVX-A12d [N=100]) or placebo (N=50), respectively. Subjects were also be stratified by age group (60 to 69 years of age and 70 to 85 years of age). The planned subject allocation to trial groups is provided in [Table 1](#).

Table 1

Group	Dosage Level	Total (N=250)*
A	IVX-A12a (unadjuvanted 150 µg RSV/ 150 µg hMPV)	100
B	IVX-A12d (150 µg RSV/ 150µg hMPV adjuvanted with MF59 [®])	100
C	Placebo [†]	50

[†] Placebo will be aqueous diluent

*Note: The stratified randomization will ensure balanced dosage level group assignment between the two age groups (60 to 69 years of age and 70 to 85 years of age, respectively).

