4.3. Determination of Sample Size

4.3.1. Main Trial Determination of Sample Size

Sample size for this trial is not based on any formal hypothesis testing. Analyses of safety and immunogenicity will be primarily descriptive in nature. An approximate total of 250 subjects (approximately 100 subjects in each of the IVX-A12 groups and 50 subjects in the placebo group) will be randomized. With 100 subjects in each IVX-A12, there is a 63.4% probability of observing at least 1 subject with an AE if the true incidence of the AE is 1% and 86.7% probability of observing at least 1 subject with an AE if the true incidence of the AE is 2%. The trial will have more than 90% power to detect a difference of 20% or more in seroresponse rate (SRR) or detect a 2-fold increase or more in GMT or GMFR (assuming standard deviation at $0.5 \log_{10}$), between the two IVX-A12 groups (or between the IVX-A12 group and placebo group), with a two-sided type-1 error rate at 0.05.

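### The overall Day 28 seroresponse differences get only unadjusted Wilson intervals; the SAP specifies no risk difference from the covariate-adjusted logistic model it already fits, so the interval is valid but modestly wider than it need be

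*SAP*

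**What the plan says.** SRR, the proportion with at least a 4-fold rise at Day 28, is among the co-primary immunogenicity endpoints (SAP 5.1.1.2). For its between-group difference, SAP 9.1.1.2 gives one method: a 95% interval "between vaccine groups with and without adjuvant and IVX-A12a versus Placebo and IVX-A12d versus Placebo will be computed using" the Wilson score method. No stratification, weighting or covariate is named.

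The same paragraph continues: "Logistic regression models will be used to further describe the IVX-A12d response to vaccination when compared to IVX-A12a", with parallel models for each active group against placebo. The explanatory variables are vaccine group, log2 baseline NAb titer, age stratum and gender. It does not say which effect measure these models report. The SRR analyses are then repeated by age subgroup, by baseline tertile and by both, with no pooling across them.

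For the other co-primary quantities the plan differs. SAP 9.1.1.1 takes the pairwise GMT and GMFR comparisons from an ANCOVA with age stratum, gender and baseline titer. Age is also a design factor: in Protocol 6.1, "subjects were stratified by age groups (60 to 69 years of age versus 70 to 85 years of age".

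SAP 4.3.1 states: "The trial will have more than 90% power to detect a difference of 20% or more in seroresponse rate (SRR"), for "approximately 100 subjects in each of the IVX-A12 groups and 50 subjects in the placebo group", "with a two-sided type-1 error rate at 0.05". It gives no underlying SRR. For the 2-fold GMT or GMFR statement it assumes an SD of 0.5 log10.

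**The concern.** Whether a subject reaches a 4-fold rise usually depends on the starting titer: a high baseline leaves less room to rise. Baseline titer is measured in everyone and is already in the SRR model, but the only SRR contrast specified on the percentage-point scale does not use it.

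An odds ratio from the logistic model would not fill the gap. It is conditional on the covariates, is not collapsible, and cannot be set against a 20-point difference. A reader would therefore see adjusted contrasts for GMT and GMFR but an unadjusted one for SRR. At stake is the width of the interval. No hypothesis is formally tested (SAP 7.1), so the intervals are what readers will use.

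**Working it through.** **1. The plan's own figure.** No base SRR is stated, so the power claim can only be checked over a range. With pooled variance, two-sided 0.05 and n = 100 per arm:

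power = Φ{[δ − 1.96·√(2p̄(1−p̄)/n)] / √[(p₁q₁ + p₂q₂)/n]}

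At 40% v 60% this is Φ{(0.20 − 1.96 × 0.0707)/0.0693} = Φ(0.886) = 81.2%. At 10% v 30% and at 70% v 90% it is 94.8%. The claim holds near the extremes of SRR and not in the middle, so precision is not abundant for active versus active.

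**2. What the stated SD implies.** Let B be log10 baseline, Y log10 Day 28 titer and F = Y − B. Then Var(F) = Var(Y) + Var(B) − 2Cov(Y,B). If Y and F both have SD 0.5, Cov(Y,B) = Var(B)/2, so the slope of Y on B is 0.5 whatever the baseline SD. The correlation of F with B is −0.5·SD(B)/0.5 = −SD(B), in log10 units: −0.4 for a baseline SD of 0.4 and −0.5 for 0.5. The baseline SD is an assumption; neither document gives one.

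**3. Crude versus standardised difference.** Trials were simulated with the SAP's covariates. The logistic model was fitted, every subject's probability predicted under each arm, and the average predictions subtracted. The variance of that estimate was divided by the variance of the crude difference.

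| Contrast | Assumed baseline SD | Variance ratio |
|---|---|---|
| A12d v A12a, 100 v 100, mid-range SRR | 0.4 | 0.89 to 0.93 |
| A12d v A12a, 100 v 100, mid-range SRR | 0.5 | 0.83 to 0.87 |
| Active v placebo, 50% v 4%, 100 v 50 | 0.5 | about 0.92 to 0.93 |

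The average crude and standardised differences agreed to within simulation error, so the target is unchanged.

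**4. Sensitivity to the assumed correlation** (baseline and fold-rise SD both 0.5, 70% v 50%). At correlations of 0, −0.3, −0.5 and −0.7 the ratio is 1.01, 0.96, 0.85 and 0.70. Only −0.5 fits a Day 28 SD of 0.5. At −0.7, Var(Y) = 0.25 + 0.25 − 0.35 = 0.15, an SD of 0.39; at 0 it is 0.50, an SD of 0.71.

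**5. Interval width.** Reading the SAP's method as the usual combination of the two single-group Wilson intervals, 70/100 v 50/100 gives 6.4 to 32.6 points, a width of 26.2. With ratio 0.854 the width is about 26.2 × √0.854 = 24.2. Over the range in the table, 1 − √0.93 = 4% and 1 − √0.83 = 9% narrower.

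**6. Power equivalent** (unpooled normal approximation, correlation −0.5). At 70 v 50 the standard error is √(0.0021 + 0.0025) = 0.0678, so power is Φ(0.20/0.0678 − 1.96) = 84%. Multiplying the standard error by √0.854 gives 0.0627 and 89%. At 60 v 40 power moves from 82% to 87%.

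**7. Age alone.** With exact balance and equal strata, an age-stratified Mantel-Haenszel difference equals the crude one. Its variance estimate is about 0.6% smaller for a 0.1 log10 age effect and about 6% smaller for 0.3 log10 (both effects assumed).

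**The case against.** The strongest reply is that an unadjusted interval beside an adjusted model is a legitimate choice in a descriptive Phase 2a trial. Randomisation makes the crude difference unbiased. That stands: this is a matter of efficiency, not validity.

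Several stronger readings are tempting, and the documents do not support them.

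- A reader might infer that the SRR analysis ignores age and baseline. It does not. Both are in the logistic model, and the differences are repeated within age strata and baseline tertiles. Only a pooled or standardised difference is missing.
- A reader might infer that the model yields odds ratios and nothing else. The SAP does not say what it reports, and table details are left to separate mock shells (SAP section 15).
- A reader might infer that the sample size rests on the 20-point difference. SAP 4.3.1 says that it rests on no formal hypothesis test.
- A reader might infer that the adjuvant question turns on SRR. SAP 9.1.1.1 assigns it to the adjusted GMT and GMFR contrasts, and Protocol 4.4 records that the unadjuvanted formulation was chosen after the Day 28 interim analysis.
- A reader might infer a gain worth 20 to 25% more subjects. That needs a slope near 0.3. With baseline and Day 28 SD of 0.5, the fold-rise SD would then be √(0.25 + 0.25 − 0.15) = 0.59, against the SAP's 0.5.

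Timing also counts. This SAP refers to an event of October 2024, after Day 28 group results had been used. Replacing the main SRR contrast now would be hard to defend; adding one, openly labelled, would not.

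**Conclusion.** The gap is real and its size is modest. For A12d versus A12a, a standardised risk difference would have about 7 to 17% lower variance, which is an interval about 4 to 9% narrower. For active versus placebo, with placebo SRR near 4% and baseline SD 0.5, the reduction is about 7 to 8%.

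These figures rest on full arms, the SAP's SD applying to both titer and fold rise, a baseline SD of 0.4 to 0.5 log10 (assumed), and SRRs in the middle of the range for the active groups (assumed). If fold rise proved unrelated to baseline there would be no gain. Nearly all of the benefit comes from baseline titer; the randomisation strata contribute little. Neither the validity of the crude interval nor any decision rule is affected.

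**What to change.** For A12d versus A12a and each single-assay SRR, report from the planned logistic model the marginal (standardised) risk difference with a delta-method or bootstrap 95% interval. Place it beside the pre-planned Wilson interval, which keeps its status, and label it as added after the Day 28 interim analysis. State that the baseline covariate is the titer from the same assay: the SAP names baseline NAb, but the outcomes include IgG. Leave out the composite responses (both strains, either strain), for which no single baseline titer is defined.

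For the placebo contrasts, where few placebo responders may make the logistic fit unstable, an age-stratified score interval is an option, though it gains little.

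The cost is one post-estimation step on a model already planned, an extra row in the SRR tables, a sentence in SAP 9.1.1.2 and an entry in SAP section 12. No new data are needed.

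### The active-versus-placebo logistic models for seroresponse have no method for zero placebo responders, and the main model names a neutralizing-antibody baseline although its outcomes include IgG

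*SAP*

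**What the plan says.** SAP 5.1.1.2 makes the proportion with at least a 4-fold rise at Day 28 a co-primary immunogenicity endpoint. SAP 9.1.1.2 analyses it in two ways for each active arm against placebo. The first is a confidence interval for the difference in proportions by Wilson's score method. The second is a model: "logistic regression models will be used to describe the response of IVX-A12a versus Placebo", with the same for IVX-A12d. No exact, penalised or other fallback is named.

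There are ten outcomes: four single-strain NAb assays, both-strain and either-strain composites for RSV and for hMPV, and two IgG assays. The models are repeated by age subgroup, by baseline tertile, and "By vaccine group and age subgroup analyses and baseline tertile". SAP 9.1.2 carries the 4-fold NAb analysis to Days 180 and 365 and adds an 8-fold NAb analysis at all post-baseline visits. The 8-fold analysis has age-subgroup repeats but no tertile repeats.

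On allocation, SAP 4.1.1 says: "Approximately 250 subjects will be randomly allocated at a ratio of 2:2:1". That plans 100, 100 and 50 subjects, with 50 on placebo.

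For the main logistic model the baseline covariate is "log2 transformed baseline NAb titer". The age-subgroup version in the same section, and the ANCOVA in SAP 9.1.1.1, refer to baseline titers without limiting them to NAb. The tertile versions carry no baseline titer.

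**The concern.** If no placebo recipient responds and some vaccine recipients do, vaccine group separates the outcome. The likelihood keeps rising as the log odds ratio grows, so no finite maximum exists. Software stops at an arbitrary point and can still print an odds ratio, a Wald interval and a p-value. The standard error grows faster than the estimate, so a strong vaccine effect can appear with a p-value close to 1. SAP 7.1 says that intervals and p-values will be presented. The only related rule, in SAP 13.2.5.2, is to show a hyphen for results that cannot be estimated. A fit that halts and returns numbers need not trigger it.

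On the covariate, a programmer who follows the main-model sentence literally would adjust an IgG response for an NAb baseline, without being told which strain. For the both-strain and either-strain outcomes the sentence does not say whose baseline to use.

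**Working it through.** **The plan's own figure.** SAP 4.3.1 claims more than 90% power for a 20-point SRR difference, two-sided 0.05, and gives no base rate. With 50 placebo and 100 vaccine subjects, placebo rate p0 and p1 = p0 + 0.20:

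- pooled rate pb = (50·p0 + 100·p1)/150
- s0 = √[pb(1 − pb)(1/50 + 1/100)]
- s1 = √[p0(1 − p0)/50 + p1(1 − p1)/100]
- power = Φ[(0.20 − 1.96·s0)/s1]

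At p0 = 5%: pb = 0.1833, s0 = 0.0670, s1 = 0.0532, power 90.2%. At 0%, 2% and 10% the power is 98.3%, 95.5% and 81.7%. The claim is therefore reproduced if placebo SRR is at most 5%, or at least about 74%, which is not a credible planning value for placebo. With the unpooled form, Φ(0.20/s1 − 1.96), power is 96.4% at 5% and 89.3% at 10%, so the limit moves to just under 10%. Either way the claim presupposes a low placebo SRR. It does not say how low.

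**Chance of no placebo responder.** This is (1 − p)^n for one outcome. The rate p is an assumption. The tertile size is 50/3, about 17. The age-by-tertile size is 50/6, about 8, and assumes an even split over the two age strata.

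| Assumed placebo SRR | n = 50 | n = 17 | n = 8 |
|---|---|---|---|
| 1% | 61% | 84% | 92% |
| 2% | 36% | 71% | 85% |
| 5% | 8% | 42% | 66% |
| 10% | 0.5% | 17% | 43% |

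Among the six single assays in the full placebo group, the expected number with no placebo responder is 6(1 − p)^50: 3.6, 2.2 and 0.5 at 1%, 2% and 5%. Among the 18 assay-by-tertile cells it is 18(1 − p)^17: 15.2, 12.8 and 7.5. Expected counts do not need the assays to be independent.

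**What the planned model prints.** The counts 0/50 placebo against 40/100 vaccine are assumed, and the fit is unadjusted. The maximum-likelihood log odds ratio rises by about 1 per iteration without limit. Stopped at a relative-gradient criterion of 1e-8, the fit gives a log odds ratio of about 17.8 (odds ratio about 5×10^7), SE about 1,268, z = 17.8/1,268 = 0.014 and Wald p = 0.99. With 60/100 vaccine responders p is also 0.99.

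**Alternatives on the same table.**

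- Score (Newcombe-Wilson) difference: 40.0 points, 95% CI 28.5 to 49.8.
- Firth: in an unadjusted 2×2 table this amounts to adding one half to each cell, (40.5/60.5)/(0.5/50.5) = 68. The profile penalised-likelihood 95% CI is 9.2 to about 8,600.
- Firth in a small cell, 0/8 against 7/17: odds ratio 12, profile CI 1.2 to about 1,660.

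**Covariate wording side by side.** The SAP 9.1.1.2 main model names the NAb baseline for outcomes that include IgG. The age-subgroup model in 9.1.1.2 and the ANCOVA in 9.1.1.1 name baseline titers generally. SAP 7.7 defines baseline tertiles for the IgG titers as well as the NAb titers, so IgG baselines are available.

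**The case against.** The strongest reply is that little inference is lost. The co-primary endpoint is the proportion, and its planned score interval against placebo is finite and valid with an empty cell. The logistic models are there to describe. SAP 7.1 tests no hypotheses. The adjuvant comparison, IVX-A12d against IVX-A12a, does not depend on placebo responders. All of this stands, and it limits the point to supportive output.

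A reader might infer that the models will usually fail. The documents do not support that, because neither gives a placebo SRR. In the full placebo group, zero cells are common at about 2% or below, uncommon at 5% and very rare at 10%. The subgroup figures also assume one rate in every tertile and an even age split. SAP 7.7 lists five overlapping age categories, and the rise probably differs by baseline level, so the real cells will vary around these values. Nor may the tertile figures be applied to the 8-fold analysis, which has no tertile repeats.

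A reader might also infer that the IgG models throughout omit their own baseline. That goes too far. The conflict is confined to the main-model sentence and is probably a wording slip. The age-subgroup wording is general, and the tertile models drop the covariate because they stratify on baseline.

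Finally, Firth does not produce narrow intervals: an upper limit of about 8,600 remains. What it gives is a usable lower limit in place of p = 0.99.

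**Conclusion.** The gap is real and worth closing, but it concerns supportive analyses. That the odds ratio is not finite with zero placebo responders and some vaccine responders is a mathematical fact, and the SAP has no method for it. How often it arises depends on an unstated rate: per assay 61%, 36% or 8% in the full placebo group and 84%, 71% or 42% in a tertile, at an assumed 1%, 2% or 5%, with age-by-tertile cells worse. Per-protocol exclusions would raise these figures somewhat: with 45 placebo subjects the full-group values are 64%, 40% and 10%. The sample-size claim makes a low placebo rate credible without fixing its value.

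The co-primary proportion and its score interval are not at risk. The covariate wording in the main model contradicts two neighbouring passages and must be reconciled. It also leaves the composite outcomes without a defined baseline.

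**What to change.** 1. For the active-versus-placebo logistic models, at 4-fold and 8-fold, specify Firth penalised likelihood with profile penalised-likelihood confidence intervals. The IVX-A12d versus IVX-A12a models need no change on this account.
2. In age-by-tertile cells, rely on the score interval for the difference in proportions, which is already planned, and drop the odds ratios against placebo.
3. In the main model of SAP 9.1.1.2, replace the NAb baseline with the log2 baseline titer of the same assay. For both-strain and either-strain outcomes, enter both strains' baselines.

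The programming is light: a model option, a covariate definition and two baseline terms for the composites. SAP section 12 indicates that tables, listings and graphs had already been completed, so some supportive tables would have to be re-run and the change recorded. The statistical price is slight shrinkage of odds ratios toward 1. Upper limits stay very wide wherever a placebo cell is empty.
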